Proprietary Information of MD Anderson

Protocol #:2018-0545

Date:2/13/2019

Page 1 of 13

Study Title: Is the Gastro™ LMA® a feasible alternative to the use of a native airway for endoscopic retrograde cholangiopancreatography (ERCP) cases?

Principal Investigator: [name]

Co-Investigator(s): [name],

Collaborator(s): [name] [name], [name], [name], [name], [name]

Statistician: [name]

Sponsor Name: Teleflex

SUMMARY TABLE

Title	Is the Gastro™ LMA® a feasible alternative to the use of a native airway for endoscopic retrograde cholangiopancreatography (ERCP) cases?
Study Size (# of patients)	30
Study Design	This is a prospective feasibility study.
Primary Objective	To evaluate the successful completion of ERCP with the LMA® Gastro™
Secondary Objectives	To evaluate the following: 1) Gastroenterologist satisfaction 2) Anesthesiologist satisfaction 3) Rate of successful placement of LMA® Gastro™ 4) To determine the ability of the LMA® Gastro™ to provide adequate oxygenation and ventilation throughout the procedure 5) To determine and describe the rate of adverse events
Inclusion Criteria	Adult patients (\geq 18 years old) undergoing elective ERCP requiring general anesthesia
Exclusion Criteria	Patients with propofol allergy Patients at increased aspiration risk Patients with abnormal head/neck pathology making LMA® Gastro™ placement difficult Patients with surgical or radiation treatment to the head/neck making LMA® Gastro™ placement difficult

	
Esophagectomy patients
 
Patients already intubated upon arrival to endoscopy suite
 
Patients undergoing Endoscopic Ultrasound (EUS)
 
Patients with BMI $\geq 35 \text{ kg/m}^2$
 
Non-English speaking patients

Study Procedures	
Pretreatment Evaluation	Eligible subjects will be identified from within the patient population of the study site. There will be no advertisements for study subjects.
On-Study Visits	
All patients meeting study criteria will have anesthesia induced with propofol
 
# of attempts to place LMA® Gastro™ will be recorded
 
Upon completion of the procedure, the gastroenterologist and anesthesiologist will complete a device satisfaction survey.

Follow-up Visits	None
End of Study Visit	None
Primary Endpoint	Successful completion of ERCP with the LMA® Gastro™ is defined as the ability to place LMA gastro within 3 attempts where completion of the procedure occurs with the LMA® Gastro™ in place.
Feasibility Definition	The study will be deemed feasible if the study can be completed without crossing any of the stopping boundaries associated with study failure provided by the Bayesian monitoring rule requiring suspension of patient accrual.
Brief Analysis Plan	The success rate will be estimated using an exact 95% confidence interval. Assuming a success rate of 90% (27/30), the limits of an exact 95% confidence interval are (0.73, 0.98). Descriptive statistics will be used to summarize all study data. Study failure, defined as inability to place the LMA gastro after 3 attempts or removal of the LMA gastro prior to the completion of the procedure for any reason, will be monitored using the following Bayesian rule: $\text{Pr}(p(F) > 0.10 \text{data}) > 0.90$, where the probability of failure is denoted by $p(F)$. Therefore, we will suspend accrual if at any time there is a greater than 90% chance that the failure rate exceeds 10%.

1. OBJECTIVES

Primary Objective: To assess the successful completion of ERCP with the LMA® Gastro™

Secondary Objectives:

- 1) To determine gastroenterologist satisfaction with the LMA® Gastro™
- 2) To determine anesthesia provider satisfaction with the LMA® Gastro™
- 3) To determine the rate of unsuccessful LMA® Gastro™ placement
- 4) To determine the ability of LMA® Gastro™ to provide adequate oxygenation and ventilation throughout the procedure.
- 5) To determine and describe the rate of adverse events

2. BACKGROUND

There is ongoing debate within the anesthesia community concerning the best way to sedate patients for ERCP. Traditionally, anesthesiologists have intubated these patients. However, many ERCP patients are now receiving propofol sedation for ERCP with a native airway. Unfortunately, it has been demonstrated in other patient populations that moderate propofol sedation frequently progresses to deep anesthesia which encompasses all the inherent airway and cardiopulmonary risks associated with propofol anesthesia.(1-5) This type of anesthetic requires constant vigilance on the part of the anesthesia provider and, at times, frequent interventions (chin lift/jaw thrusts or placement of an oral airway or nasal trumpet). Furthermore, 28% of patients experience oxygen saturations of < 90% and a small percentage (0.2%) experience aspiration pneumonia which may lead to significant morbidity and mortality.(6)

Management of a native airway for overweight or obese individuals or for longer procedures is particularly challenging.(7,8) The alternative to propofol sedation with a native airway is either endotracheal intubation (which is more invasive for the patient, increases anesthesia time, and is not without its own risks, such as prolonged muscle paralysis and dental damage) or moderate sedation by the endoscopist (which requires significant attention from the endoscopist to do safely and effectively, perhaps making completion of their therapeutic procedure more difficult). Osborn et al. demonstrated that it was feasible to perform ERCP with a laryngeal mask airway by displacing the LMA tube to the lower left side of the mouth.(9) LMAs are generally placed easily by trained practitioners, with a maximum of 3 attempts allowable, as described by the Difficult Airway Society.(10)

[figure not shown]
The LMA® Gastro™ represents a novel device with the ability to facilitate direct endoscopic access via the integrated endoscopic channel. Although the utility for esophagogastroduodenoscopy has been demonstrated(11), a similar feasibility study has not been conducted for ERCP procedures. The utility of the LMA® Gastro™ may be less for ERCPs, as ERCP procedures require multiple small movements to enable cannulation of the bile duct and frequent advancement or retraction of the endoscope in order to successfully complete the procedure. It is possible that the presence of the LMA tube will make these maneuvers more challenging. The goal of this study is to determine the feasibility of the LMA® Gastro™ for ERCP.

3. BACKGROUND DEVICE INFORMATION

The LMA® Gastro™ has separate gastric and airway access. Respiratory depression from sedative drugs and airway obstruction requiring intervention are known risks associated with endoscopic

procedures, with studies demonstrating that hypoxemia can occur in 11-50% of cases. The LMA® Gastro™Airway with Cuff Pilot™ Technology from Teleflex is the only laryngeal mask specifically designed to give clinicians control of their patients' airways while facilitating direct endoscopic access via the integrated endoscopic channel. With the airway in place, clinicians can monitor end tidal CO₂ for patient safety. The LMA® Gastro™Airway is indicated for airway management in adult patients.

The LMA® Gastro™Airway is a single-use laryngeal mask with a di(2-ethylhexyl)phthalate (DEHP)-free silicone cuff and airway tube. The silicone cuff is soft and flexible, and conforms to patient anatomy to create an effective oropharyngeal seal. The LMA® Gastro™Airway also features Cuff Pilot Technology – an integrated, cuff pressure indicator that constantly monitors cuff pressure detecting changes resulting from fluctuations in temperature, nitrous oxide levels and movements within the airway. It provides at-a-glance feedback, highlighting changes that could affect patient safety so that adjustments can be made when necessary.

4. STUDY DESIGN

This is a prospective single arm feasibility study.

5. DISCUSSION OF STUDY POPULATION

5.1 Study Characteristics

a) **Number of Subjects:** This study will enroll 30 patients. We anticipate a screen failure rate of

30-50%.

5.2 Inclusion and Exclusion Criteria

a) Inclusion Criteria

- Adult patients (≥ 18 years old) undergoing elective ERCP with general anesthesia.

b) Exclusion Criteria

- Patients with propofol allergy
- Patients at increased aspiration risk
- Patients with abnormal head/neck pathology preventing LMA® Gastro™ placement
- Patients with surgical or radiation treatment to the head/neck making LMA® Gastro™ placement difficult
- Esophagectomy patients
- Patients already intubated upon arrival to endoscopy suite
- Patients undergoing Endoscopic Ultrasound (EUS)
- Patients with $BMI \geq 35 \text{ kg/m}^2$
- Non-English speaking patients

6. SUBJECT IDENTIFICATION, RECRUITMENT AND CONSENT

6.1 Method of Subject Identification and Recruitment

Eligible subjects will be identified from within the patient population of the study site by a member of the research team. Advertisements for study subjects are not anticipated.

6.2 Consent Process

Subjects deemed eligible to participate in the study will be explained in detail the purpose, nature and procedures of the study, as well as the potential risks, benefits and alternatives. They will be given a consent form to read and if they so choose, to discuss with friends, family, and other clinicians. They will be invited to ask questions and, after all questions are answered to their satisfaction, invited to sign the consent form. The Principal Investigator or another member of the research team will participate in the consenting process to ensure the subject has full understanding of the procedure and risks. No study-specific procedure will be performed before the consent form is signed.

All consents will be signed electronically within the medical record on a MD Anderson password protected computer.

6.3 Costs to the Subject

None

6.4 Payment for Participation

There will be no payments for participation in the study.

6.5 Return of Individual Research Results

Individual research results will not be provided back to the subject.

7. METHODS AND STUDY PROCEDURES

7.1 Pretreatment Evaluation

The PI/Co-PI/research coordinator of the study will evaluate the inclusion/exclusion criteria. Patients will be approached while in the preoperative area to discuss participation in the study. The PI/Co-PI/research coordinator will ensure that patients are properly informed about the study. All study related data will only be collected after the PI or Co-PI approves patient enrollment in the study and the patient has signed the consent.

7.2 Procedure

Prior to patient induction, the appropriate size LMA® Gastro™ will be chosen based upon manufacturer recommendations. The LMA® Gastro™ will be fully deflated and the posterior aspect will be lubricated with KY jelly as per manufacturer instructions prior to insertion.

Upon arrival to the procedure room, all standard of care monitoring will be performed, including pulse oximetry, noninvasive blood pressure monitoring, EKG, and capnography. The patient will be preoxygenated with 100% oxygen via full face mask in the supine position prior to induction of general anesthesia. Pre-oxygenation will be administered for 3 minutes of normal tidal volume breathing or for 8 deep breaths over one minute, or until end expiratory oxygen reaches 90%.

Once pre-oxygenation is complete, patients will be induced with 1mg/kg 1% lidocaine and 1-4 mg/kg propofol. Upon loss of the patients lash reflex, the LMA® Gastro™ will be placed in the patient's oropharynx. The cuff should be inflated until the cuff pilot indicator line is within the green zone. Appropriate placement will be confirmed with end tidal CO₂ and adequate tidal volumes of at least 4-5 cc/kg. The LMA® Gastro™ will be secured using the manufacturer provided adjustable holder and strap. Following placement confirmation, sedation will be titrated to achieve deep to general anesthesia using a propofol infusion at 50-300 mcg/kg/min. Insufficient sedation with propofol may be supplemented with inhalational anesthetics or opioids.

After securing the airway, the patient will be positioned on the fluoroscopy table in the prone position with head facing to the right (although occasionally patient may be repositioned in the left lateral decubitus or supine position) to facilitate the ERCP. Positioning is at the discretion of the gastroenterologist. After the patient is positioned, the anesthesiologist will again confirm that the LMA® Gastro™ is positioned properly before allowing the procedure to begin. During the procedure, the patient may receive positive pressure ventilation keeping airway pressures \leq 20 mmHg or the patient may maintain spontaneous ventilation with or without ventilator support, as

long as adequate minute ventilation (≥ 5 L/min) and appropriate end tidal CO₂ (< 45 mmHg) is maintained.

A standard sideviewing duodenoscope measuring 11.3mm in maximum diameter will be lubricated with KY jelly by the gastroenterologist, coating the full length of the endoscope that will be inserted into the LMA® Gastro™.

Should the LMA® Gastro™ impede completion of the procedure, the anesthesiologist will remove the LMA® Gastro™ and either proceed with a native airway or place an endotracheal tube. This decision will be at the discretion of the anesthesiologist.

7.3 Data Collected from EMR

- Demographics (e.g. BMI, age, gender)
- Comorbidities
- Indication for procedure
- Dosing of medications
- Information regarding anesthetic management
- Information about the ERCP procedure

7.4 Additional Data Collected by Research Coordinator

- Number of attempts required to place the LMA® Gastro™ (See Appendix 2)
- Removal of the LMA® Gastro™ prior to completion of the procedure (See Appendix 2)
- Any adverse events (See Appendix 2)
- Gastroenterologist device satisfaction survey (See Appendix 3)
- Anesthesiologist device satisfaction survey (See Appendix 3)

7.5 Special Instructions and Definitions of Events

- LMA® Gastro™ placement attempt is defined as passage of the LMA® Gastro™ into the oropharynx
- The gastroenterologist and anesthesiologist device satisfaction surveys will be filled out independently and privately

8. SUBJECT WITHDRAWALS

Subjects may be withdrawn from the study for the following reasons:

- 1). Subject non-compliance with study procedures
- 2). Unacceptable adverse events (safety or tolerability)
- 3). The subject may withdraw from the study at any time and for any reason
- 4). Clinician decision that it is in the best interest of the subject to withdraw from the study

9. SAFETY AND REPORTABLE EVENTS

9.1 Adverse Event Definition

An adverse event is any symptom, sign, illness, or experience which develops or worsens during the course of the study, whether or not the event is considered related to investigational product. This includes a change in a subject's condition or laboratory results, which has or could have a deleterious effect on the subject's health or well-being. An Adverse Event that is related to the investigational device may be referred to as an Adverse Device Effect (ADE).

Unanticipated Adverse Device Effect (UADE): Any device related adverse event, the nature or severity of which is not consistent with or listed in the applicable product information (e.g., instructions for use, subject informed consent document, subject information brochure [if applicable], promotional literature) or any other unanticipated serious problem associated with a device that relates to the rights, safety, or welfare of subjects.

Expected Adverse Events

Abrasion to lips, tongue, or oral mucosa

Conversion to endotracheal intubation or native airway

Small amount of blood tinged sputum

Sore throat

9.2 Serious Adverse Event

A serious adverse event is defined as any adverse medical experience that results in any of the following outcomes:

- Death
- Is life-threatening
- Requires inpatient hospitalization or prolongation of existing hospitalization
- Results in persistent or significant disability/incapacity
- Is a congenital anomaly/birth defect
- Requires medical or surgical intervention to prevent permanent impairment or damage

9.3 Recording Adverse Events

The site study staff will assess adverse events by recording all voluntary complaints of the subject and by assessment of clinical and laboratory features.

All adverse events, whether observed by the investigator, elicited from or volunteered by the subject, should be documented. Each adverse event will include a brief description of the experience, the date of onset, the date of resolution, the duration and type of experience, the severity, the relationship to investigational product (i.e. the device), contributing factors, and any action taken with respect to the study device.

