9.4 Responsibilities for Reporting Serious Adverse Events

The Investigator should record all serious adverse experiences that occur during the study period in the appropriate source documents and/or AE log as applicable. The study period for

reporting serious adverse events (e.g. from the time of signing consent to final study visit) should be indicated, who needs to be notified and the time frame for notification. If there are any specific reporting forms to be completed, this should be indicated here. The Investigator will comply with regulations and IRB policy regarding the reporting of adverse events.

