15. APPENDIX

- 11.1 Calendar of Events
- 11.2 RCF for Intraprocedural events
- 11.3 LMA® Gastro™ satisfaction surveys

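### No time point or standard question is set for adverse events after the procedure, so sore throat may be under-ascertained in the adverse event rate

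*Combined protocol and SAP*

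**What the plan says.** - **Objective.** Section 1 lists as secondary objective 5: "To determine and describe the rate of adverse events". Section 5.1 sets the size: "This study will enroll 30 patients".
- **How AEs are found.** Section 9.3 states: "The site study staff will assess adverse events by recording all voluntary complaints of the subject and by assessment of clinical and laboratory features". The next sentence says that events seen by the investigator, or "elicited from or volunteered by the subject", should be documented, and the section goes on to ask for onset, resolution, duration, severity and relationship to the device.
- **Where they are written down.** Section 7.4 has the research coordinator record any AE on Appendix 2. Section 15 titles that form "RCF for Intraprocedural events".
- **When.** The Summary Table gives None for both follow-up visits and an end-of-study visit. The calendar in Appendix 1 marks CRF completion and medical record documentation post-op, without a time.
- **Reporting window.** Section 9.4 says the period for SAE reporting should be indicated and offers an example, "from the time of signing consent to final study visit". No period is filled in.
- **Expected events.** Section 9.1 lists four: "Abrasion to lips, tongue, or oral mucosa", conversion to another airway, a small amount of blood-tinged sputum, and sore throat.

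**The concern.** A rate is interpretable only if every patient is assessed in the same way over the same period. Here the text sets neither. Section 7.2 keeps patients under deep to general anesthesia during the procedure, so a sore throat can be reported only after waking. Whether it enters the data then depends on whether the patient mentions it or someone happens to ask, and on when.

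Any resulting error would be downward: the reported sore-throat rate would be too low, and its confidence interval would not reflect that. Section 9.3 also asks for the resolution date and duration of each event, which are hard to obtain for a sore throat that outlasts recovery when there is no later contact and no stated window.

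**Working it through.** **1. Each expected event against the routes the plan describes**

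| Expected event (9.1) | Route in the plan | Risk of being missed |
|---|---|---|
| Airway conversion | Device removal item, 7.4 | None: it is recorded during the procedure |
| Oral abrasion | Clinical assessment, 9.3 | Weaker: staff can see it |
| Blood-tinged sputum | Clinical assessment, 9.3 | Weaker: staff can see it |
| Sore throat | Patient report, volunteered or elicited, 9.3 | Present: no scheduled question or time |

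**2. The plan's own interval**

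Sections 12.1 and 12.2 use Clopper-Pearson exact 95% limits. For x events in n patients, the lower limit is the 0.025 quantile of Beta(x, n − x + 1) and the upper limit is the 0.975 quantile of Beta(x + 1, n − x). For 27/30 this gives (0.7347, 0.9789), which rounds to the stated (0.73, 0.98). I apply the same method to an AE rate.

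**3. Illustration of an undercount**

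The documents give no AE rate and no capture fraction, so both are assumed. Let p be the true sore-throat rate, c the fraction captured, and n = 30 (full accrual). The observed count is then X ~ Binomial(30, p × c), with expected count 30 × p × c. At p = 30% and c = 50%, that is 30 × 0.30 × 0.50 = 4.5 instead of 9.

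The interval lies wholly below p when its upper limit is below p. Upper limits for n = 30 are:

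- 0 events 0.116
- 1 event 0.172
- 2 events 0.221
- 3 events 0.265
- 4 events 0.307
- 6 events 0.386
- 7 events 0.423

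So this happens when X ≤ 1 for p = 20%, X ≤ 3 for p = 30% and X ≤ 6 for p = 40%. For p = 10% it cannot happen, because even 0/30 has an upper limit above 0.10.

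Probability that the interval lies wholly below the true rate:

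| True rate p | Condition | c = 100% | c = 75% | c = 50% | c = 25% |
|---|---|---|---|---|---|
| 10% | none | 0 | 0 | 0 | 0 |
| 20% | X ≤ 1 | 1% | 5% | 18% | 55% |
| 30% | X ≤ 3 | 1% | 7% | 32% | 82% |
| 40% | X ≤ 6 | 2% | 16% | 61% | 97% |

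The effect is material if sore throat is common and poorly captured. If it is rare, the interval is too wide for the loss to show.

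**The case against.** The best defence is that Section 9.3 is broader than its phrase about voluntary complaints. The same sentence adds clinical and laboratory assessment, and the next names observed and elicited events. The two sentences can both be followed, so they do not conflict. The calendar provides for post-op CRF completion, so recording is not confined to the anesthetised period. The Appendix 2 form is not in the available text, and it may contain a sore-throat item.

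Most of this stands. A reader might infer that AEs are collected only as voluntary complaints, only during the procedure, and that oral abrasion and sore throat will certainly be undercounted. The documents do not support that: they name other routes and a post-op CRF, the form's items cannot be judged from its title, and staff can see an abrasion.

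What the defence does not supply is a schedule. Saying that elicited events should be documented does not say that anyone elicits them, when, or with what question. A post-op mark in the calendar gives no time either. Even if the form has a sore-throat item, the available sections do not say when or how the patient is asked.

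A reader might also link an undercount to the statement in Section 10.3 that sore throat is less likely than with intubation. That is a risk/benefit statement, not an objective, and this single-arm study has no intubation group, so it cannot test the comparison.

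**Conclusion.** The point holds as a risk, not as a demonstrated bias. The available text describes no uniform post-procedure AE assessment and no closed AE or SAE window. Sore throat is the expected event most exposed.

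The size cannot be derived from the documents. It rests on an assumed true rate and capture fraction, on full accrual of 30, and on the Section 12.2 interval being used for AE rates. Across the assumed values, the chance that the interval misses the true rate on the low side runs from zero (true rate 10%) to 97% (true rate 40%, a quarter captured). The unfilled SAE period in Section 9.4 needs no assumption: it is plain on the page.

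Only a descriptive secondary objective is affected. The primary endpoint and the Bayesian monitoring rule use placement and device removal, not these events. This is a cheap improvement worth making, and it does not threaten the study's main conclusion.

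**What to change.** - **Section 9.3.** Replace reliance on voluntary complaints with wording such as: *Before discharge from recovery, every patient is asked the same short set of questions on the expected events (sore throat; injury to lip, tongue or mouth; blood-tinged sputum) and one open question. Presence and severity are recorded on the post-op CRF.* Name who asks. If the Appendix 2 form already has these items, refer to it and add the timing.
- **Section 9.4.** Replace the template wording with one fixed end of the AE/SAE window for all patients, for example that contact plus the EMR record to discharge.
- **Section 12.2.** Report elicited and volunteered events separately, with all patients in whom placement was attempted as the denominator.

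**Cost.** A few items on the post-op CRF already in the calendar and about a minute of coordinator time per patient, with no extra visit. The reported AE rate will probably be higher. Sore throat that starts after discharge would still be missed, and this should be stated as a limitation.
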